**Table 5.1-2: On-Treatment Assessments - Nivolumab 240mg/Q2 weeks CA209627**

Procedure	Cycle 1 Day 1 (C1D1) (First dose)	Each Cycle (every 2 weeks) on Day 1	Notes:
Efficacy Assessments			
Radiographic Tumor Assessment		See notes	
See Appendix 4 (RECIST 1.1 Guidelines) for details regarding imaging methodology requirements and assessments
 
Radiographic tumor assessment must be performed on Week 8 (<math>\pm</math> 5 days), prior to the next cycle, at Week 16 prior to the start of 480 mg dosing, and at Week 28 prior to dosing. Cycles beyond Week 16 may be <math>\pm</math> 5 days.

Clinical Drug Supplies			
Administer Study Drug	X	X	
Within 3 days from vial allocation, the subject must receive the first dose of study medication. Subjects may be dosed no less than 12 days between doses and no more than 3 days from the scheduled dose. Contact with IVRS for drug vial assignment.

**Table 5.1-3: On-Treatment Assessments - Nivolumab 480mg/Q4 weeks CA209627**

Procedure	Each Cycle (every 4 weeks) on Day 1	Notes
Safety Assessments		
Targeted Physical Examination	X	Targeted examination must include at a minimum the following body systems: Cardiovascular, Gastrointestinal, and Pulmonary. Weight must be collected. Within 3 days before dosing
Vital Signs	X	Temperature, BP, RR, and HR. Obtain vital signs within 3 days before dosing.
ECOG Performance Status	X	See Appendix 2 for ECOG scale
Adverse Events Assessment	X	Assessed using NCI CTCAE v. 4.0.
Serious Adverse Event Assessments	X	Assessed using NCI CTCAE v. 4.0.
Review of Concomitant Medications	X	
Laboratory Tests	X	On-study local laboratory assessments should be done within 3 days prior to dosing for every cycle and to include: CBC with differential, Chemistry panel including LFTs (ALT, AST, total bilirubin, alkaline phosphatase), BUN or serum urea level, creatinine, Ca, Na, K, Cl, phosphate, LDH, and glucose.
Thyroid Function Testing	X	TSH (reflex to free T3 and free T4 if abnormal result) to be performed every 8 weeks ( $\pm$ 1 week).
Pregnancy Test	X	Serum or urine every 4 weeks regardless of dosing schedule.
Efficacy Assessments		
Radiographic Tumor Assessment	Every 12 weeks	See Appendix 4 (RECIST 1.1 Guidelines) for details regarding imaging methodology requirements and assessments  Radiographic tumor assessment must be performed q12 weeks $\pm$ 5 days. Timing of radiographic assessments is based on timing from first dose.

**Table 5.1-3: On-Treatment Assessments - Nivolumab 480mg/Q4 weeks CA209627**

Procedure	Each Cycle (every 4 weeks) on Day 1	Notes
Clinical Drug Supplies		
Administer Study Drug	X	Within 3 days of schedule dose. Contact with IVRS for drug vial assignment.

**Table 5.1-4: Follow-Up Assessments - All Subjects CA209627**

Procedure	Follow-Up Visits X01 (Day 35) ( $\pm 7$ Days) and X02 (Day 100) a ( $\pm 7$ Days) after last dose	Survival Follow-Up Visits b Every 12 weeks	Notes
Safety Assessments			
Targeted Physical Examination	X		Targeted examination must include the Cardiovascular, Gastrointestinal, and Pulmonary body systems and examination to specific malignancy To assess for potential late emergent study drug related findings.
Vital Signs	X	X	
Adverse Events and Serious Adverse Events Assessment	X		All AEs and SAEs must be collected up to 100 days after study drug discontinuation. SAEs that relate to any later protocol specified procedure must be collected.
Review of Medical History and Subsequent Cancer Therapy Information	X	X	
Laboratory Tests	X		CBC with differential, Chemistry panel including LFTs (ALT, AST, total bilirubin, alkaline phosphatase), BUN or serum urea level, creatinine, Ca, Na, K, Cl, phosphate, LDH, and glucose.
Thyroid Function Testing	X		TSH (reflex to free T3 and free T4 if abnormal result)
Pregnancy Test	X		Serum or urine

**Table 5.1-4: Follow-Up Assessments - All Subjects CA209627**

Procedure	Follow-Up Visits X01 (Day 35) ( $\pm 7$ Days) and X02 (Day 100) a ( $\pm 7$ Days) after last dose	Survival Follow-Up Visits b Every 12 weeks	Notes
Efficacy Assessments			
Radiographic Tumor Assessment	See notes		Only for subjects without progression and no longer on study therapy. If subject starts subsequent treatment, no assessment required  Subjects with a history of brain metastasis may have surveillance MRI approximately every 12 weeks or sooner if clinically indicated
Subject Status			
Survival Status	X	X	Every 3 months after X02; may be accomplished by visit or phone contact, to update survival information and assess subsequent anti-cancer therapy.

NOTES:

a Subjects must be followed for at least 100 days after last dose of study treatment. Follow-up visit #1 occurs approximately 35 days ( $\pm 7$  days) after the last dose or coinciding with the date of discontinuation ( $\pm 7$  days) if date of discontinuation is greater than 30 days after last dose. Follow-up visit #2 occurs approximately 100 days ( $\pm 7$  days) from last dose

b Survival Follow-up visits to occur every 3 months from Follow-up Visit 2. At the time of this request, each subject will be contacted to determine their survival status unless the subject has withdrawn consent for all contact. Vital signs not required if follow-up is performed via telephone contact.

### **5.1.1      Retesting During Screening or Lead-in Period**

Retesting of laboratory parameters and/or other assessments within any single Screening or Lead-in period will be permitted (in addition to any parameters that require a confirmatory value).

Any new result will override the previous result (ie, the most current result prior to Randomization) and is the value by which study inclusion will be assessed, as it represents the subject's most current, clinical state.

Laboratory parameters and/or assessments that are included in [Table 5.1-1](#), Screening Procedural Outline may be repeated in an effort to find all possible well-qualified subjects. Consultation with the Medical Monitor may be needed to identify whether repeat testing of any particular parameter is clinically relevant.

## **5.2      Study Materials**

- National Cancer Institute Common Terminology Criteria for Adverse Events NCI CTCAE version 4.0
- BMS-936558 Nivolumab Investigator Brochure
- Laboratory Manuals for collection and handling of blood and tissue specimens
- Pharmacy Binder
- Site manual for operation of interactive voice response system, including enrollment worksheets
- Serious Adverse Event CRFs/eCRFs

## **5.3      Safety Assessments**

At screening, a medical history will be obtained to capture relevant underlying conditions. The screening examinations should include weight, height, ECOG Performance Status, blood pressure (BP), heart rate (HR), respiration rate (RR), and temperature.

Screening local laboratory assessments should be done within 14 days prior to treatment and are to include: CBC with differential, Chemistry panel including LFTs (ALT, AST, total bilirubin, alkaline phosphatase), BUN or serum urea level, creatinine, Ca, Na, K, Cl, phosphate, LDH, glucose, albumin, and thyroid panel including TSH, free T3, and free T4.

Screening pregnancy tests for WOCBP must be performed within 24 hours prior to the initial administration of study drug.

The following screening local laboratory assessments should be done prior to treatment: Hepatitis B and C testing (HBV sAg and HCV Ab or HCV RNA).

While on-study the following local laboratory assessments will occur within 3 calendar days prior to each dose: CBC with differential, chemistry panel including LFTs (ALT, AST, total bilirubin, alkaline phosphatase), BUN or serum urea level, creatinine, Ca, Na, K, Cl, phosphate, LDH, glucose.

Thyroid function testing (TSH; reflexive fT3 and fT4 if abnormal during on-treatment testing) is to be done every 6 weeks (every 3 doses) for subjects receiving nivolumab at 240 mg q2w, then every 8 weeks ( $\pm$  1 week) for subjects receiving nivolumab at 480 mg q4w (every other dose). If the patient demonstrated an active endocrinopathy during the nivolumab 240 mg dosing period, then thyroid function testing will be performed every 6 weeks ( $\pm$  1 week) at the discretion of the treating physician.

On treatment pregnancy tests should be performed as per the schedule in the Time & Events table.

Subjects will be evaluated for safety if they have received any study drug. Toxicity assessments will be continuous during the treatment phase as well as during the first 2 safety follow-up visits. Once subjects reach the survival follow-up phase, either in-person visits or documented telephone calls/email correspondence to assess the subject's status are acceptable.

Adverse events and laboratory values will be graded according to the NCI-CTCAE version 4.

The start and stop time of the study therapy infusions and any interruptions or infusion rate reductions should be documented.

Physical examinations are to be performed as clinically indicated. If there are any new or worsening clinically significant changes since the last exam, report changes on the appropriate non-serious or serious adverse event page.

On treatment local laboratory assessments are to be completed within 3 calendar days prior to dosing.

Additional measures, including non-study required laboratory tests, should be performed as clinically indicated or to comply with local regulations. Laboratory toxicities (eg, suspected drug induced liver enzyme evaluations) will be monitored during the follow-up phase via on site/local labs until all study drug related toxicities resolve, return to baseline, or are deemed irreversible.

If a subject shows pulmonary-related signs (hypoxia, fever) or symptoms (eg, dyspnea, cough, fever) consistent with possible pulmonary adverse events, the subject should be immediately evaluated to rule out pulmonary toxicity, according to the suspected pulmonary toxicity management algorithm in the BMS-936558 Nivolumab Investigator Brochure and [Appendix 3](#).

Some of the assessments referred to in this section may not be captured as data in the eCRF. They are intended to be used as safety monitoring by the treating physician. Additional testing or assessments may be performed as clinically necessary or where required by institutional or local regulations.

### **5.3.1      *Imaging Assessment for the Study***

Images will be collected centrally and may be reviewed by blinded independent central review (BICR) at a later date, or at any time during the study. Image acquisition guidelines and submission process will be outlined in the CA209-627 Imaging Manual to be provided by the core lab.

Any additional imaging that may demonstrate tumor response or progression (including scans performed at unscheduled timepoints and/or at an outside institution) should be collected for RECIST 1.1 tumor assessment and submitted to the BICR.

Study evaluations will take place in accordance with [Table 5.1-1](#), [Table 5.1-2](#), [Table 5.1-3](#), and [Table 5.1-4](#) according to RECIST 1.1. CT with IV contrast are the preferred imaging modalities for assessing radiographic tumor response. In cases where contrast is contraindicated, a non-contrast scan will suffice. Screening (baseline) tumor assessments of, chest, abdomen, pelvis, and all known / suspected sites of disease are to be performed prior to first dose. Subsequent assessments should include chest, abdomen, pelvis, and all known / suspected sites of disease using the same imaging method and technique as was used at baseline.

For evaluating CNS metastasis, brain MRI is the required imaging method, and assessment is required during screening in subjects with a known history of treated brain metastases. All known sites of disease (including CNS) should be assessed at baseline and subsequent assessments using the same imaging method and technique. If more than 1 method is used at screening, then the most accurate method according to RECIST 1.1 should be used when recording data, and should again be used for all subsequent assessments. Bone scan, PET scan, or ultrasound is not adequate for assessment of RECIST 1.1 response. Previously treated CNS metastases are not considered measurable lesions for purposes of RECIST 1.1 determined response. Subjects with a history of brain metastasis should have surveillance MRI approximately every 12 weeks or sooner if clinically indicated.

Radiographic tumor response will be assessed at Week 8 ( $\pm$  5 days), Week 16 ( $\pm$  5 days), and Week 28 ( $\pm$  5 days), then every 12 weeks ( $\pm$  5 days) until disease progression, beyond progression, lost to follow-up, or withdrawal of consent. Tumor assessments for all subjects should continue as per protocol even if dosing is interrupted. Tumor measurements should be made by the same investigator or radiologist for each assessment whenever possible. Change in tumor measurements and tumor response to guide ongoing study treatment decisions will be assessed by the investigator using the RECIST 1.1 criteria (see [Appendix 4](#) for details of RECIST 1.1). Independent adjudication will resolve equivocal interpretations of imaging results.

*Local radiologic assessment of tumor measurements will be used during the study for clinical management and investigator-assessed disease progression using RECIST 1.1 criteria. The same imaging modality used in screening must be used in all subsequent imaging assessments. Any incidental findings of potential clinical relevance that are not directly associated with the objectives of the protocol should be evaluated and handled by the study investigator as per standard medical/clinical judgment.*

## **5.4 Efficacy Assessments**

### **5.4.1 Objective Response Rate (ORR)**

The primary endpoint is investigator-assessed ORR in all treated subjects. See [Section 8.3.1](#).

Please see Appendix 4 for RECIST 1.1.

### 5.4.2 Secondary Efficacy Assessments

Secondary endpoints are DOR, TTR, CBR, and OS at 1 year. See [Section 8.3.2](#) for the definitions of these endpoints.

100% of the time, the *hedgehog* is a hedgehog, and the *cat* is a cat. The *hedgehog* is not a *cat*, and the *cat* is not a *hedgehog*.

For more information, contact the Office of the Vice President for Research and the Office of the Vice President for Student Affairs.

—

1  

© 2019 Pearson Education, Inc.

1. **What is the primary purpose of the proposed legislation?**

2. **How will the proposed legislation affect the current regulations?**

3. **What are the potential consequences for non-compliance with the proposed legislation?**

4. **What are the proposed penalties for non-compliance?**

5. **What is the timeline for the proposed legislation to take effect?**

6. **What are the proposed requirements for reporting and disclosure?**

7. **What are the proposed requirements for record-keeping and retention?**

8. **What are the proposed requirements for training and education?**

9. **What are the proposed requirements for enforcement and inspection?**

10. **What are the proposed requirements for public notice and comment?**

Figure 1. The effect of the number of clusters on the classification accuracy of the proposed model.

© 2013 Pearson Education, Inc.

100% of the time, the system is able to correctly identify the target class for the test samples.

1

## **5.7        Retention of Tissue for Additional Research**

All residual blood and tissue samples will be retained by the BMS Biorepository for additional research purposes. No additional sampling is required. Additional research retention is mandatory for all subjects, except where prohibited by local laws and regulations. Details of sample collection and processing will be provided to the site in the procedure manual.

## **5.8        Outcomes Research Assessments**

Not applicable.

## **5.9        Other Assessments**

Not applicable.

## **6            ADVERSE EVENTS**

An *Adverse Event (AE)* is defined as any new untoward medical occurrence or worsening of a preexisting medical condition in a clinical investigation subject administered study drug and that does not necessarily have a causal relationship with this treatment. An AE can therefore be any unfavorable and unintended sign (such as an abnormal laboratory finding), symptom, or disease temporally associated with the use of study drug, whether or not considered related to the study drug.

The causal relationship to study drug is determined by a physician and should be used to assess all adverse events (AE). The causal relationship can be one of the following:

Related: There is a reasonable causal relationship between study drug administration and the AE.

Not related: There is not a reasonable causal relationship between study drug administration and the AE.

The term "reasonable causal relationship" means there is evidence to suggest a causal relationship.

Adverse events can be spontaneously reported or elicited during open-ended questioning, examination, or evaluation of a subject. (In order to prevent reporting bias, subjects should not be

questioned regarding the specific occurrence of one or more AEs.) Care should be taken not to introduce bias when collecting AE and/or SAEs. Inquiry about specific AEs should be guided by clinical judgement in the context of known adverse events, when appropriate for the program or protocol.

Sponsor or designee will be reporting adverse events to regulatory authorities and ethics committees according to local applicable laws including European Directive 2001/20/EC and FDA Code of Federal Regulations 21 CFR Parts 312 and 320.

Immune-mediated (IM) adverse events are AEs consistent with an immune-mediated mechanism or immune-mediated component for which non-inflammatory etiologies (eg, infection or tumor progression) have been ruled out. IMAEs can include events with an alternate etiology which were exacerbated by the induction of autoimmunity. Information supporting the assessment will be collected on the participant's case report form.

## **6.1        Serious Adverse Events**

A **Serious Adverse Event (SAE)** is any untoward medical occurrence that at any dose:

- results in death
- is life-threatening (defined as an event in which the subject was at risk of death at the time of the event; it does not refer to an event which hypothetically might have caused death if it were more severe)
- requires inpatient hospitalization or causes prolongation of existing hospitalization (see **NOTE** below)
- results in persistent or significant disability/incapacity
- is a congenital anomaly/birth defect
- is an important medical event (defined as a medical event(s) that may not be immediately life-threatening or result in death or hospitalization but, based upon appropriate medical and scientific judgment, may jeopardize the subject or may require intervention [eg, medical, surgical] to prevent one of the other serious outcomes listed in the definition above.) Examples of such events include, but are not limited to, intensive treatment in an emergency room or at home for allergic bronchospasm; blood dyscrasias or convulsions that do not result in hospitalization.) Potential drug induced liver injury (DILI) is also considered an important medical event. (See [Section 6.6](#) for the definition of potential DILI.)
- Admission for administration of anticancer therapy in the absence of any other SAEs

Suspected transmission of an infectious agent (eg, pathogenic or nonpathogenic) via the study drug is an SAE.

Although pregnancy, overdose, cancer, and potential drug induced liver injury (DILI) are not always serious by regulatory definition, these events must be handled as SAEs. (See [Section 6.1.1](#) for reporting pregnancies).

Any component of a study endpoint that is considered related to study therapy (eg, death is an endpoint, if death occurred due to anaphylaxis, anaphylaxis must be reported) should be reported as SAE (see Section 6.1.1 for reporting details).

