**NOTE:**

The following hospitalizations are not considered SAEs in BMS clinical studies:

- a visit to the emergency room or other hospital department < 24 hours, that does not result in admission (unless considered an important medical or life-threatening event)
- elective surgery, planned prior to signing consent
- admissions as per protocol for a planned medical/surgical procedure
- routine health assessment requiring admission for baseline/trending of health status (eg, routine colonoscopy)
- medical/surgical admission other than to remedy ill health and planned prior to entry into the study. Appropriate documentation is required in these cases
- admission encountered for another life circumstance that carries no bearing on health status and requires no medical/surgical intervention (eg, lack of housing, economic inadequacy, caregiver respite, family circumstances, administrative reason)
- Admission for administration of anticancer therapy in the absence of any other SAEs (applies to oncology protocols)

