### **6.1.1      *Serious Adverse Event Collection and Reporting***

Sections 5.6.1 and 5.6.2 in the BMS-936558 Nivolumab Investigator Brochure represent the Reference Safety Information to determine expectedness of serious adverse events for expedited reporting. Following the subject's written consent to participate in the study, all SAEs, whether related or not related to study drug, must be collected, including those thought to be associated with protocol-specified procedures. All SAEs must be collected that occur during the screening period and within 100 days of the last dose of nivolumab. If applicable, SAEs must be collected that relate to any later protocol-specified procedure (eg, a follow-up skin biopsy).

The investigator must report any SAE that occurs after these time periods and that is believed to be related to study drug or protocol-specified procedure.

An SAE report must be completed for any event where doubt exists regarding its seriousness.

If the investigator believes that an SAE is not related to study drug, but is potentially related to the conditions of the study (such as withdrawal of previous therapy or a complication of a study procedure), the relationship must be specified in the narrative section of the SAE Report Form.

SAEs, whether related or not related to study drug, and pregnancies must be reported to Sponsor or designee within 24 hours of awareness of the event. SAEs must be recorded on the SAE Report Form; pregnancies on a Pregnancy Surveillance Form (electronic or paper forms). The preferred method for SAE data reporting collection is through the eCRF. The paper SAE/pregnancy surveillance forms are only intended as a back-up option when the eCRF system

is not functioning. In this case, the paper forms are to be transmitted via email or confirmed facsimile (fax) transmission to:

**SAE Email Address:** Refer to Contact Information list.

**SAE Facsimile Number:** Refer to Contact Information list.

For studies capturing SAEs through electronic data capture (EDC), electronic submission is the required method for reporting. In the event the electronic system is unavailable for transmission, paper forms must be used and submitted immediately. When paper forms are used, the original paper forms are to remain on site.

**SAE Telephone Contact** (required for SAE and pregnancy reporting): Refer to Contact Information list.

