7.6.2 Serious Adverse Events

Serious adverse events will be summarized by tumor group:

- Overall summary of SAEs by worst CTC grade (grade 1, 2, 3, 4, 5, unknown) presented by SOC/PT using the 30-day and repeated using the 100-daysafety window
- Overall summary of SAEs by worst CTC grade (any grade, grade 3-4, grade 5) presented by SOC/PT using the 30-day and repeated using the 100-day safety window and for AEs with extended follow-up. This table will be restricted to events with incidence greater or equal to 1% in any tumor group.
- Overall summary of drug-related SAEs by worst CTC grade (any grade, grade 3-4, grade 5) presented by SOC/PT using the 30-day and repeated using the 100-day safety window and AEs with extended follow-up

By-subject SAE listing will be provided for the All Enrolled Subjects population.

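### Protocol 6.1 lists admission for anticancer therapy both as an SAE criterion and as a hospitalization that is not an SAE, and nothing in the documents says which governs.

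*Protocol*

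**What the plan says.** Protocol 6.1 opens by saying that an SAE "is any untoward medical occurrence that at any dose" meets one of the bullets that follow. One of these is that the event "requires inpatient hospitalization or causes prolongation of existing hospitalization", and that bullet sends the reader to the NOTE below. The last bullet is "Admission for administration of anticancer therapy in the absence of any other SAEs". It carries no reference to the NOTE.

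The NOTE begins: "The following hospitalizations are not considered SAEs in BMS clinical studies". Its last bullet is "Admission for administration of anticancer therapy in the absence of any other SAEs (applies to oncology protocols" (the source closes the bracket after these words).

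Protocol 6.1.1 requires SAEs to be reported within 24 hours of awareness, whether or not they are related to study drug, and collected to 100 days after the last dose. It adds: "An SAE report must be completed for any event where doubt exists regarding its seriousness".

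Protocol 8.3.2.5 makes SAE incidence in each tumor group a safety measure. SAP 7.6.2 says "Serious adverse events will be summarized by tumor group" and presents SAEs by system organ class, preferred term and worst grade, on a 30-day window and again on a 100-day window. Of one all-causality table it says: "This table will be restricted to events with incidence greater or equal to 1% in any tumor group".

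**The concern.** A definition that decides what sites must report should give one answer for one event. Here a site that reads to the end of the definition finds the admission among the criteria, and a site that reads to the end of the NOTE finds it excluded. Both texts are current, and this is an oncology protocol, so the tag in the NOTE applies.

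What is at stake is the SAE count. Subjects may start another therapy within 100 days of their last nivolumab dose. If one is admitted for that purpose and the site follows the definition bullet, the admission enters the database as an SAE although nothing untoward need have happened. Because the groups are small, even one such record is visible in a group's SAE percentage.

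**Working it through.** The plan states no figure that depends on this bullet, so there is nothing to reproduce. The check is a comparison of texts, followed by one line of arithmetic for scale.

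**Step 1: the two lists side by side**

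| | Protocol 6.1, definition | Protocol 6.1, NOTE |
|---|---|---|
| What the lead-in does | Makes each bullet a criterion for an SAE | Makes each bullet a hospitalization that is not an SAE |
| Last bullet | Admission to give anticancer therapy, no other SAE present | The same, with a tag for oncology protocols |
| Link to the other list | Only the inpatient-hospitalization bullet points to the NOTE | None |

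The admission falls under both headings. The NOTE qualifies the inpatient-hospitalization criterion by express reference. It does not expressly qualify the anticancer-therapy bullet, which stands as a separate criterion.

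**Step 2: is there a rule that decides?**

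- Protocol 6.1.1 says what to do in doubt (report) but not which bullet governs. A site that sees both bullets has reason for doubt, so the rule leans towards a report.
- SAP 7.6.2 tabulates SAEs and gives no definition of its own.
- SAP 7.6 refers to a Core Safety SAP, which was not available for this check. Whether it treats such admissions at analysis is unknown. It would not change what Protocol 6.1 tells sites.

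**Step 3: which list does the sentence belong to?**

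The bullet does not complete the lead-in of the definition grammatically, whereas it fits the NOTE. Its condition that no other SAE be present is how one writes an exclusion. The oncology tag appears only in the NOTE. All three point to a NOTE bullet copied into the wrong list.

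**Step 4: scale**

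Inputs: a usual maximum of 25 subjects per group (Protocol 8.1; larger at the sponsor's discretion) and a 1% display threshold (SAP 7.6.2).

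- SAE incidence counts subjects, so one subject whose only SAE in the window is such an admission adds 1/n.
- At n = 25: 1/25 = 4%, that is 4 points, above the 1% threshold.
- 1/n is below 1% only when n is above 100, four times the usual cap. In groups smaller than 25 the contribution is larger than 4 points.

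The number of such subjects is not given, so this cannot be turned into a total.

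**The case against.** The best defence is that a careful reader would not be misled. The definition applies only to something untoward, and an admission made solely to deliver treatment is arguably not that. The NOTE is categorical and singles out oncology protocols. On this view the bullet is a slip that sites would read past. Much of this stands: it limits how many sites would report such admissions. It does not remove the conflict, because the definition does list the admission and the doubt rule favours reporting it.

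The analysis also limits the harm. SAEs are tabulated on a 30-day as well as a 100-day window, and the shorter one is less exposed to later therapy. Drug-related SAEs have their own table, and an admission to receive another treatment would ordinarily be judged unrelated to nivolumab. Safety is summarized descriptively, and the success and futility rules use response rate only. These points stand as well.

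A reader might go further and infer that SAE incidence is overstated by a large amount, or most in tumor groups that progress early. The documents support neither. They give no rate of inpatient admission for later therapy. A large overstatement would also need most such subjects to have no other SAE in the window, and their sites to follow the definition bullet. As to early progression, Protocol 4.5.4 allows treatment beyond progression, so progression does not by itself mark the start of another therapy.

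A reader might also infer uneven reporting between sites. That is possible but not shown: the doubt rule pushes every site in the same direction.

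**Conclusion.** The contradiction is real and unresolved in the current text. It is a minor inconsistency in a reporting definition, not a choice of analysis. If it has an effect, the likelier direction is over-reporting of SAEs rather than missed safety events.

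The total effect cannot be computed. The only scale that the documents support is 4 points of SAE incidence per affected subject in a group of 25. This assumes that the subject has no other SAE in the window and that the site reported the admission. It would fall mainly in the 100-day all-causality tables, on the assumption that such admissions are for therapy given after nivolumab and are judged unrelated to it. The documents do not show that any such SAE has been reported, and no efficacy conclusion depends on the point.

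**What to change.** Reconcile the two lists in Protocol 6.1: delete the anticancer-therapy bullet from the SAE definition and keep it only in the NOTE.

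Before the SAE tables are run, query any SAE reported solely on this ground. Where the site confirms that no other event met a criterion, correct the classification. Where another event did, keep that event as the SAE. Subsequent cancer therapy is already collected at the follow-up visits (Protocol Table 5.1-4), so the candidate records can be found by cross-check.

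The cost is one deleted bullet, by amendment or administrative letter, and one data query. No table, sample size or decision rule changes.
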